6.2.2 Inverse Probability of Treatment Weighting (IPTW)

Patients who received larotrectinib in the SCOUT trial will likely differ in various underlying characteristics from those who are recorded in the external historical control cohorts. These characteristics are listed above as potential confounders (See [sections 6.1.2](#) and [6.1.4](#)). The analyses will need to be adjusted for these patient characteristics to avoid biased results.

An adjustment methodology using a PS will be employed to reduce the effects of measured confounding variables in the interpretation of the treatment effect (larotrectinib *versus* external historical group). A PS can be seen as an overall “balancing score”, that is calculated for each patient based on his or her measured underlying characteristics.

The PS will be obtained from a logistic regression model with dependent variable: larotrectinib group (yes/no). Covariates will be taken from the list of potential baseline confounders above. The predicted probabilities of receiving larotrectinib from this logistic regression model will form the PS for each patient. Example SAS code is as follows:

```
proc logistic data=temp;
class cat1 cat2 ... / param=ref;
model tx (event = "Laro") = cat1 cat2 var1 var2 ...;
output out=temp2 pred=propensity;
run;
```

where all categorical variables appear in the `class` statement in addition to the `model` statement. Predicted probabilities in the code example above appear in `temp2`.

Therefore, the weight assigned to each patient is the inverse probability of being in a certain group conditioning on these baseline covariates. For larotrectinib patients, this is the reciprocal of the PS, while for external comparator patients this is the reciprocal of one minus the PS. These weights are stabilized by multiplying by the marginal probability of treatment that was actually received, which avoids very large weights being assigned to larotrectinib patients with a very low PS or to comparator patients with a PS close to 1.

The selection of covariates for retention in the logistic regression model for the PS will be considered. Brookhart et al [3] showed in simulations that: (1) including a variable in the PS model related only to survival but not to treatment group decreased the variance of the treatment effect without affecting bias; (2) failure to include a true confounder (i.e. related to both treatment group and survival) led to a biased estimator; (3) the inclusion of a variable related only to treatment group increased the variance of the treatment effect without altering bias. Similar results were reported by Andrillon, Pirracchio and Chevret [4], in small samples, who confirmed that matching on a PS model including instrument variables (associated with treatment allocation) increased the bias of the estimated treatment effect compared to matching on a prognostic model or on the true confounder model.

Two PS models will be considered:

1. **SLR model:** The core subset of variables in [section 6.1.4](#), comprising the prognostic factors identified by the SLR (, IRS group, age) and time from locally advanced/metastatic disease diagnosis to initiation of treatment.
2. **Full model:** All covariates in [1] and additional covariates listed in [section 6.1.2](#):
 - a. Additional demographic variables: sex;
 - b. Additional covariates on disease history: time from initial diagnosis to first dose of treatment tumor location;
 - c. Covariates on treatment-related information: prior surgical treatments for cancer, prior radiation treatment for cancer, prior systemic treatments.

The SLR only identified IRS group as a significant prognostic factor, and we have augmented the SLR model above with age (due to its clinical importance) and locally advanced versus metastatic disease stage (expert consensus on its likely significance despite lack of data). The failure of the SLR to identify other prognostic factors may in part be explained by the small sample sizes limiting the

power of those studies referred to in the report. Notwithstanding these data deficiencies, it does seem unlikely that the analysis could be biased by unmeasured confounders. However, this will be explored as detailed in [section 6.5](#) to allay any concerns. Balance metrics presented in the following section will help to discriminate between these two approaches for the PS model.

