6.1.4 Core subset of prognostic variables

IRS initial resectability classification

IRS group was the most studied prognostic factor in the literature in terms of its impact on overall survival (OS). IRS Stage has 4 groups, but most of the studies (Orbach 2010, Cecchetto 2001, Sulkowski 2013) compared the impact of IRS I *versus* IRS II or IRS I *versus* IRS II/III on clinical outcomes. Those studies suggested that IRS I may be an indicator of better prognosis, either in terms of OS or event-free survival (EFS), than IRS II or III. No studies investigated the impact of IRS IV (which corresponds to metastatic disease stage) on clinical outcomes compared to other IRS groups.

The IRS initial resectability classification was not collected in SCOUT study, however given it is reported as a prognosis factor in the literature, in order to allow to feature it in the PS model, IRS for SCOUT IFS patients will be derived from their disease status. Locally advanced disease corresponds as per medical expert opinion (PI. [name]) to IRS III and metastatic disease to IRS IV (as per IRS definition).

Locally advanced *versus* metastatic disease stage

We have no knowledge of locally advanced *versus* metastatic disease stage being studied on clinical outcomes due to a lack of metastatic patients included in any IFS studies. However, the broad expert consensus is that metastatic disease stage is likely to have a significant effect on endpoints in comparison to locally advanced patients. Given IRS initial resectability classification already captures the stage of the disease, the impact of disease stage will be already accounted for and an additional variable locally advanced vs metastatic disease stage is not needed to feature in the PS model.

Primary Tumor Localization

Two studies explored the impact of primary tumor localization (axis *versus* extremity) on clinical outcomes (Orbach 2010[11], Cecchetto 2001). Only Orbach 2010 explored its impact on EFS, which did not reveal a statistical difference between tumor locations. Both studies found consistent results that tumor localization did not have an impact on OS. However, the Cecchetto study did include both infantile and adult fibrosarcoma patients, and results from this study may not be fully representative of the current study. Therefore, tumor location will not form part of the core prognostic factors for the PS model.

Tumor Size

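### The SAP contradicts itself on whether disease stage is in the propensity model, and gives an IRS rule for SCOUT only, so this covariate may be defined differently by arm

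*SAP*

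**What the plan says.** **Stage.** SAP 6.1.4 argues that IRS group already carries stage, so that "an additional variable locally advanced vs metastatic disease stage is not needed to feature in the PS model". The numbered SLR model in SAP 6.2.2 agrees; it is described as "comprising the prognostic factors identified by the SLR (, IRS group, age) and time from locally advanced/metastatic disease diagnosis to initiation of treatment". The paragraph after that list says the opposite: the SLR model has been augmented with age and with "locally advanced versus metastatic disease stage (expert consensus on its likely significance despite lack of data". The full model is built on all SLR-model covariates, so it takes over whichever reading applies.

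**IRS.** SAP 6.1.4 states: "The IRS initial resectability classification was not collected in SCOUT study". To use it anyway, "IRS for SCOUT IFS patients will be derived from their disease status", with locally advanced disease mapped "to IRS III and metastatic disease to IRS IV (as per IRS definition". The same section notes "IRS Stage has 4 groups", and that the literature mostly compared group I with group II or with II/III. On the remaining group it says: "No studies investigated the impact of IRS IV (which corresponds to metastatic disease stage) on clinical outcomes compared to other IRS groups". The SAP does not say how IRS is obtained for Curie and CWS controls, at what time point, or which groups occur there.

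**The concern.** IRS group is the only factor that the SLR found prognostic, and it sits in both candidate propensity models. In SCOUT it is not the initial resectability class but a relabelling of disease status. It therefore cannot express the contrast that justifies its use (group I against II or II/III). It also carries no tumour-size information, although 6.1.4 drops size on the ground that size enters through IRS.

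If the controls keep a recorded initial class, one covariate name covers two definitions. A control recorded as I or II then has no SCOUT patient to be compared with, and weighting cannot create one. At stake is whether the weights adjust for prognosis or partly for a coding difference. The primary comparison has few events: on the SAP's own inputs, 49 × 0.04 + 42 × 0.19 = 9.94 are expected.

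**Working it through.** **Inputs.** 49 SCOUT and 42 control patients (SAP section 4); balance guideline 10% (6.2.3); SCOUT IRS limited to III/IV (6.1.4). The number c of controls in group I or II is not in the documents, so it is an assumption shown over a range. The SAP gives no IRS distribution, so it has no figure of its own to reproduce on this point. Its 51% power, which uses the same sample sizes, does reproduce: k = 49/42 = 1.167, m = 9.94, √(1.167 × 9.94) × 0.75 / (1.167 × 0.25 + 1) − 1.96 = 0.017, power 50.7%.

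**Step 1: stage, place by place.**
- 6.1.4: out.
- 6.2.2, numbered SLR list: not listed.
- 6.2.2, following paragraph: in.
- 6.2.5, covariates of the exact-matching analysis: not listed.

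**Step 2: does the stage contradiction alone change the weights?** If IRS is categorical and IV means metastatic in both arms, the stage indicator equals the IRS IV indicator. With no I/II patients, intercept + IV + stage is three columns of rank 2. In illustrative fits (10 of 49 and 4 of 42 metastatic, assumed), adding stage changed propensity scores by about 1e-9 at most. The contradiction changes numbers only if IRS and stage diverge, for example IRS at diagnosis and stage at index.

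**Step 3: effect of c controls in group I/II.** Take a propensity model saturated in IRS.
- SCOUT has none in I/II, so the fitted score there is 0 and each such control has stabilised weight (42/91)/(1 − 0) = 0.46.
- At any other level with n₁ SCOUT patients and n₀ controls, the control weights sum to (42/91)(n₁ + n₀).
- All control weights therefore sum to (42/91) × 91 = 42, and the weighted I/II share is q = c(42/91)/42 = c/91, against 0 in SCOUT.
- Standardised difference = q/√(q(1 − q)/2) = √(2c/(91 − c)); unweighted it is √(2c/(42 − c)).

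| c of 42 | Weighted control share | Unweighted difference | Weighted difference |
|---|---|---|---|
| 0 | 0% | 0 | 0 |
| 1 | 1.1% | 22.1% | 14.9% |
| 2 | 2.2% | 31.6% | 21.2% |
| 4 | 4.4% | 45.9% | 30.3% |
| 8 | 8.8% | 68.6% | 43.9% |

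**Step 4: robustness.** With 51 SCOUT patients, the total in the line-of-therapy table in SAP section 7 (19 + 32), c = 1 gives √(2/92) = 14.7%. The SAP states no formula for the standardised difference. If the unweighted standard deviation is the denominator, c = 1 gives (1/91)/√((1/42)(41/42)/2) = 10.2%, at the line, and c = 2 gives (2/91)/√((2/42)(40/42)/2) = 14.6%. Adding age and time to the model would shift the control share somewhat; the SCOUT share stays 0.

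**Step 5: planned safeguards (6.2.5).** Truncation at weight 10 never touches a weight of 0.46. Trimming drops patients below the 2.5th percentile of the larotrectinib scores. In the illustrative fits (c = 0 to 8) that percentile was 0.51 to 0.57, so controls with scores near 0 go. This happens only in the sensitivity analysis.

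**The case against.** The strongest reply is that no I/II controls need exist. SAP 5.1.1 limits both arms to locally advanced or metastatic disease, and by the correspondence in 6.1.4 such patients are III or IV. A reader might infer that the SAP prescribes different coding by arm, or that IRS cannot be balanced. The documents support neither: they give a rule for SCOUT and are silent on controls. This part of the objection stands.

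It does not close the question. The covariate is an initial classification. Protocol 9.3.4 lists stage at diagnosis with local disease as a category, and separately a date of evolution to advanced disease. A control could thus have been local at diagnosis, carry a recorded I or II, and still be eligible. A SCOUT patient with the same history would be III or IV if current status is used, and 32 larotrectinib patients started at second line or later. The general baseline rule in SAP 4.5 (last value before treatment start) does not say what to do with an initial class.

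The stage sentence may well be leftover text, since the other places agree and the list has a stray comma. That makes it easy to correct, not harmless to leave.

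The diagnostics in 6.2.3 would reveal an imbalance, and trimming should remove its source. Both points are fair, but the primary analysis would keep these patients. On direction, 6.1.4 suggests group I may do better, so such controls would tend to favour the control arm and work against larotrectinib.

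**Conclusion.** Two defects hold on the text alone. The SAP both excludes and includes stage in the SLR model, and hence in the full model. It also defines IRS by proxy in SCOUT with no matching rule or time point for controls.

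The size depends on an unstated count. With no I/II controls, and IV equal to metastatic in both arms, there is no I/II imbalance and the two variables are redundant. With one such control of 42, the weighted difference is about 15% (about 10% with an unweighted denominator), so the 10% guideline is reached or passed. This assumes a propensity model in IRS alone and controls that keep a recorded class. Differences of 30% or 44% correspond to 4 or 8 such controls and are illustrations, not estimates. Non-comparability of the arms is a possibility that the SAP leaves open, not something it states. The change is worth making because it takes an arm-dependent definition out of both candidate models at almost no cost.

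**What to change.** - State one rule and one time point for both arms: code controls as III or IV from disease status by the SCOUT rule. This is in effect a single stage covariate; use it in the SLR model, the full model and the exact-matching analysis.
- Correct the sentence in SAP 6.2.2 so that stage enters once, and count it once in the balance metrics of 6.2.3, since 6.1.2 lists stage and IRS separately.
- Tabulate the recorded IRS of controls, by source, before any outcome analysis.
- Repeat the primary analysis without any control recorded as I or II. This overlaps with the 5% trimming but isolates the cause.

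The cost is SAP wording and one further sensitivity analysis. The downside is that recorded resectability detail in controls no longer enters the weights, and neither does tumour size through IRS. The loss on size is limited, because the derived SCOUT variable carries no size information in any case.

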6.2.3 IPTW Diagnostics

The distribution of the PS will be graphed for both larotrectinib and control groups. Ideally, there will be no extreme PS and good overlap of treatment and control. Sensitivity analyses described below will address any concerns about outliers in the distribution of PS.

For the two PS models detailed above (SLR and full model), standardized differences between larotrectinib and comparator groups will be computed. A graph will show the absolute standardized difference for each of the baseline covariates in [section 6.1.2](#), comparing larotrectinib and historical control, for both the unweighted and weighted samples. A standardized difference of 10% or below is considered a reasonable guideline for demonstrating sufficient balance between the two groups.

For continuous covariates in the PS model, side-by-side boxplots comparing the distribution of the covariate between the two treatment groups will be presented for both unweighted and weighted samples. After weighting, the boxplots for larotrectinib and comparator should appear similar.

A measure of the overlap in the distribution of a covariate for both groups after applying IPTW weights can be calculated using the overlapping coefficient (OVL) for each baseline covariate, per Andrillon, Pirracchio and Chevret [5]. The OVL is defined as the common area under two probability density curves, and is used here as a measure of agreement between the two treatment groups. For each continuous variable, kernel density estimates (KDE) are found for each group on a common set of grid points, and the value of the minimum KDE is calculated. The area under the minimum of the two density curves is computed based on the trapezoidal rule of integration. This can be calculated using PROC KDE in SAS, and referring to the SAS blog on difference of density estimates[10]. When calculating the OVL for the weighted sample, a WEIGHT statement can be added to the KDE procedure that incorporates the IPTW weights. For categorical covariates within the unweighted sample, the OVL is simply the sum of the minimum proportions (for the 2 groups) across all categories. For the weighted OVL, the group proportions for each category are replaced by their weighted equivalent.

Therefore, per Belitser et al[6], a median OVL can be calculated across all baseline covariates ([section 6.1.2](#)) to get an overall measure of balance for SLR and full models. We also consider a weighted average, where weights are chosen to emphasize that balance on strong prognostic factors is more important than on factors that are only weakly related to the primary outcome. We use the following weights[6]

$$w_i = 1 + |\log(\widehat{HR}_{x_i y})| - \frac{1}{I} \sum_{k=1}^I |\log(\widehat{HR}_{x_k y})|$$

where $\widehat{HR}_{x_i y}$ is the hazard ratio for covariate x_i in relation to time-to-event primary outcome y in a univariate Cox proportional hazards (PH) model. This assumes there are also a total of I covariates considered in [section 6.1.2](#). Therefore, covariate i is upweighted if the strength of association between the factor and outcome y is greater than average, in terms of the coefficient of the Cox PH model. Conversely, covariates whose strength of association with the outcome is below the average will be

downweighted. The median and weighted OVL value for SLR and full PS models, along with other diagnostic outputs detailed above, will be used to choose the appropriate PS model for use with the primary outcome model in [section 6.2.4](#) and other secondary endpoints. We can decide whether the SLR model is sufficient, or whether there is an advantage in expanding the set of baseline covariates in the PS model.

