makes it closer to the global population ([Austin 2014](#); [Thoemmes 2016](#); [Cenzer 2020](#)). In addition, the IPTW method allows one to estimate the average treatment effect (ATE). In this sense, it can mimic a randomized trial, which is designed to provide an unbiased estimation of the ATE ([Austin 2014](#)). In contrast, a conventional matching approach (e.g. matching pairs of treated and control subjects on the logit of the propensity score) is restricted to estimating the average treatment effect in the treated (ATT). ATT would only be expected to equal ATE in a randomized control trial setting. The IPTW method makes it possible to reduce bias by correcting each patient's contribution by a weight equal to the reciprocal of the probability of receiving the treatment that was actually received. For larotrectinib patients, this is the reciprocal of the propensity score, while for comparator patients this is the reciprocal of one minus the propensity score. These weights are stabilized by multiplying by the marginal probability of treatment that was actually received, which avoids very large weights being assigned to larotrectinib patients with a very low propensity score or to comparator patients with a propensity score close to 1. Austin and Stuart recommend keeping "design" and "analysis" separate, and not using the outcome data in the propensity score process. Therefore, the balancing and analysis steps will be two completely distinct tasks ([Austin and Stuart 2015](#)).

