9.7.3 IPTW method

The choice of covariates for the propensity score model will be finalized at a later date. IPTW analysis will be adopted for all time-to-event endpoints, and also for response endpoints (ORR, DCR). If possible, all available covariates will be included in the propensity score model. A SLR will be conducted to identify and quantify the known prognostic factors (see details in [Section 9.3.4](#)). If possible, the analyses will be adjusted based on all those prognostic factors. Every effort will be made to decrease bias by including covariates that are associated with outcome, or are true confounders (associated with both exposure and outcome), as demonstrated by Piracchio et al. ([Piracchio 2012](#)) in simulations involving small sample sizes ([Cenzer 2020](#)).

For all baseline covariates included in the propensity score model, standardized differences between larotrectinib and comparator groups will be computed. A graph will show the absolute standardized difference for each of the covariates, comparing larotrectinib and comparator, for both the unweighted and weighted samples. A standardized difference of 10% is commonly considered the threshold below which demonstrates reasonable balance between the two groups. Greater imbalance may be more acceptable for covariates that are weakly prognostic than for covariates that are strongly prognostic ([Austin and Stuart 2015](#)). The list of covariates with strong prognostic impact will be refined based on a SLR.

For continuous covariates, side-by-side boxplots comparing the distribution of the covariate between the two groups will be presented for both unweighted and weighted samples. After weighting, the boxplots for larotrectinib and comparator should appear similar.

The distribution of the propensity score will be graphed for both larotrectinib and control groups. Ideally, there will be no extreme propensity scores and good overlap of treatment and control. If there are markedly different propensity score distributions between the two groups, then it may be more challenging to provide valid treatment group comparisons.

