As of the 20 July 2021 cut-off, there are 49 SCOUT IFS patients available for analysis. The pooled external cohorts from Curie and CWS will comprise N=42. Therefore, the power calculations in the protocol can be updated with current information on sample size as follows:

- N=49 IFS patients for SCOUT
- N=42 for pooled external control cohorts
- pE=0.04 (probability of failure in SCOUT) and pC=0.19 (probability of failure in control) per protocol assumptions
- Optimistic scenario of a strong treatment effect (HR=0.25)
- Power=51%
- Power cannot exceed 62.9% for N=49 for SCOUT and an unlimited number of subjects in the external arm

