4.5 Data Rules

All documented therapies will be coded using the World Health Organization – Drug Dictionary (WHO-DD). Medical history and diagnoses will be coded using the latest Medical Dictionary for Regulatory Activities (MedDRA) version coding system.

Unless otherwise specified, baseline value is defined as last non-missing value on or prior to first dose of larotrectinib for the SCOUT study, or as last non-missing value on or prior to start date of chemotherapy (first line) for the external historical control cohorts.

Calculation of months is derived as: 1 month = 30.4375 days.

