6.1.3 Systematic Literature Review

A SLR was conducted in order to identify and quantify the impact of prognostic factors on the primary endpoint. The report found that there was a lack of evidence in the literature on prognostic factors that might have an influence on clinical outcomes for patients with IFS.

The SLR identified only 5 studies, and due to the rarity of the disease all studies had a small sample size leading to a high degree of imprecision in the results. The report has highlighted the following core subset of prognostic factors for inclusion into the PS model.

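### SAP 6.2.3 lets the study's own primary outcome help choose the propensity score model, against protocol 9.7.2 and without being listed as a change in SAP section 7

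*SAP*

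**What the plan says.** Protocol 9.7.2 cites a recommendation to separate design from analysis by "not using the outcome data in the propensity score process. Therefore, the balancing and analysis steps will be two completely distinct tasks". Protocol 9.7.3 accepts that imbalance is more tolerable on weakly prognostic covariates, and says where prognostic strength is to come from: "The list of covariates with strong prognostic impact will be refined based on a SLR".

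SAP 6.2.2 sets out two candidate PS models. The SLR model has IRS group, age and time from advanced disease to treatment. The Full model adds sex, tumour location, time from initial diagnosis, and prior surgery, radiotherapy and systemic treatment.

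SAP 6.2.3 then gives the diagnostics for choosing between them. One is an OVL averaged over the section 6.1.2 covariates with weights w_i = 1 + |log HR_i| − mean |log HR|, where HR_i comes from a univariate Cox model of the primary endpoint. A covariate "is upweighted if the strength of association between the factor and outcome y is greater than average". On its use: "The median and weighted OVL value for SLR and full PS models, along with other diagnostic outputs detailed above, will be used to choose" the PS model for the primary outcome model and the secondary endpoints.

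SAP section 7 lists three changes: the population for the complementary analysis, the replacement of the index-date sensitivity analysis by exact matching, and an added first-line subgroup. It mentions neither outcome-based weights nor protocol 9.7.2.

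**The concern.** The protocol presents outcome-free balancing as a safeguard. In a non-randomised comparison with an external control it is one of the few protections against a model choice that follows the results. Under SAP 6.2.3 the analyst must fit models to the primary endpoint before the PS model is settled.

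The choice reaches far. The chosen model supplies the weights for the primary hazard ratio and for the secondary endpoints (SAP 6.3), and it defines the matched pairs in the unmeasured-confounder analysis (SAP 6.5).

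The metric is also under-specified. The SAP does not state which patients enter the Cox fits, whether treatment is a term or a stratum, what happens when a hazard ratio diverges, or how the diagnostics are combined if they disagree.

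**Working it through.** **1. Text comparison.** Protocol 9.7.2 excludes outcome data from the propensity score process. The weights in SAP 6.2.3 are a function of the primary outcome and feed the PS model choice. The two cannot both be followed. The SAP does not say in words that the Cox models use study data, but that is the natural reading: the hazard ratios are written as estimates for the primary endpoint, and no outside source is named. The literature could not supply them either. SAP 6.1.3: "The SLR identified only 5 studies, and due to the rarity of the disease all studies had a small sample size". SAP 6.2.2: "The SLR only identified IRS group as a significant prognostic factor".

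**2. Expected events.** Inputs from SAP section 4: 49 SCOUT patients, 42 controls, and "pE=0.04 (probability of failure in SCOUT) and pC=0.19 (probability of failure in control) per protocol assumptions".
- SCOUT: 49 × 0.04 = 1.96. Controls: 42 × 0.19 = 7.98. Total m = 9.94.
- Check against the SAP's own power figure: k = 49/42 = 1.167; √(k·m) × 0.75 / (k × 0.25 + 1) = 3.405 × 0.75 / 1.292 = 1.977; Φ(1.977 − 1.960) = 50.7%. The SAP states 51%, so the inputs are read correctly.
- SAP Table 2 shows 8 controls with second-line or later therapy. A subsequent systemic treatment is a primary event, so about 8 control events looks like a floor. More events would narrow the ranges below.

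**3. Precision of the hazard ratios behind the weights.** For a binary covariate of prevalence p with no effect, SE(log HR) ≈ 1/√(m·p·(1−p)).
- p = 0.5: SE = 1/√2.485 = 0.634; 95% range exp(±1.96 × 0.634) = 0.29 to 3.47.
- p = 0.1 (assumed): SE = 1/√0.895 = 1.057; range 0.13 to 7.94. The chance of no event in that level is 0.96^4.9 × 0.81^4.2 = 0.34, and the hazard ratio then diverges.
- Under a normal approximation the average |log HR| of a null covariate is SE × √(2/π): 0.51 at p = 0.5 and 0.84 at p = 0.1. The rarer null covariate thus gets a weight about 0.33 higher on average, from imprecision alone.

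**4. Can the cohort difference enter the weights?** Take prior systemic treatment, assumed to have no effect of its own. SAP 4.5 takes a control's baseline value "as last non-missing value on or prior to start date of chemotherapy (first line) for the external historical control cohorts", from which it follows (by inference; the SAP does not say so) that it is zero in controls. Table 2 puts 32 of 51 larotrectinib patients at second line or later. The table's total is 51, not 49, so the proportion is applied to 49: 49 × 32/51 = 30.7 exposed.
- Pooled fit without treatment: exposed events 30.7 × 0.04 = 1.23. The other 60.3 patients have 9.94 − 1.23 = 8.71 events, risk 0.1446. Expected HR ≈ ln(0.96)/ln(1 − 0.1446) = 0.26. With 32 of 49 exposed it is also 0.26 (0.257). Over assumed risks of 0.04 to 0.10 in SCOUT and 0.19 to 0.30 in controls, it runs from 0.16 to 0.59. This association is the cohort difference alone.
- Fit stratified by cohort (31 exposed, 18 unexposed in SCOUT): that route closes, but the estimate rests on about 2 events. The chance of no event in at least one level is 0.96^31 + 0.96^18 − 0.96^49 = 0.282 + 0.480 − 0.135 = 0.63.

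**5. What the planned analyses would show.** Trimming and truncation (SAP 6.2.5) keep the chosen PS model. Exact matching fixes the SLR-model covariates and starts controls at the matched line; 34 of 42 controls had first line only, so at most 8 can have a different index date. The unweighted hazard ratio uses no PS model. None of these gives the hazard ratio at the primary index date under the PS model not chosen.

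**The case against.** The case on the other side has weight. Both candidate models are pre-specified and neither contains an outcome term. The metric uses covariate-outcome, not treatment-outcome, associations, and comes from a cited source. The other diagnostics (standardised differences, PS plots, boxplots, median OVL) use no outcome data. Protocol 9.7.3 itself says that balance matters more on prognostic covariates, the protocol leaves analysis details to the SAP, and the results are declared exploratory. Exact matching covers much of the gap if the Full model is chosen, because it shows a result with the SLR covariates and nearly the same index dates, although the up to 8 controls who shift are ones with a primary event. The prior-treatment example is also mainly an overlap problem that the outcome-free plots would reveal.

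All of this stands, and it limits the point. It does not remove the conflict. Protocol 9.7.3 points to the literature review for the list of strongly prognostic covariates, and a citation for the metric does not reconcile it with 9.7.2. With no rule for combining diagnostics, the weighted OVL could decide the choice when the others disagree.

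A reader might infer that the primary hazard ratio is biased towards larotrectinib, or that the weighted OVL determines the PS model. The documents support neither: it is one input among several, and step 4 concerns a single weight under an unstated fit, not the choice or its result.

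**Conclusion.** The conflict with protocol 9.7.2 is real, rests on the text and is not declared in SAP section 7. Its consequence is a weakened safeguard and a noisy selection metric. With about 10 planned events, the hazard ratio of a null covariate at 50% prevalence spans about 0.29 to 3.47. Leakage of the cohort difference into the weights is conditional on pooled Cox fits without a treatment term, which the SAP leaves open. The event count is a planning figure, and the 10% prevalence and the alternative risks are assumptions. No change in the model chosen or in the primary hazard ratio has been shown. Protection is partial: pre-specified candidates, unweighted hazard ratios and exact matching help, but the result under the other PS model at the primary index date is not planned. The point is worth fixing before analysis; it does not invalidate the design.

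**What to change.** - Take the weighted OVL out of the model choice. Choose between the SLR and Full models on standardised differences, PS overlap and the unweighted median OVL, all already planned, and date the choice before any treatment-outcome analysis.
- Report the primary hazard ratio under the PS model not chosen as a sensitivity analysis.
- State in the SAP that control second-line use was already known when it was written (Table 2), so outcome-blindness is only partly restored.
- If the weighted OVL is kept, show it as descriptive only, and list and justify it in SAP section 7 as a departure from protocol 9.7.2. Also state which patients enter the Cox fits, whether treatment is included, and how a diverging hazard ratio is handled.

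Cost: SAP wording and one extra run. The downside is that the balance summary no longer reflects prognostic strength estimated in the study data.
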